## Chronic Prostatitis Cohort (CPC) Study PROTOCOL

### 1. BACKGROUND

Chronic prostatitis is a disabling condition affecting an untold number of men of all ages and ethnic origins. As early as 1980, the National Ambulatory Care Survey reported 20 office visits/1,000 men/year for symptoms compatible with prostatitis (1). Although by one estimate, 50% of men will suffer from symptoms of prostatitis at some point in their lives, most symptomatic men do not have bacterial prostatitis, for which the treatment and management is usually successful (2). Therefore, as noted by Krieger *et al.* (3), the most common syndromes for men with chronic prostatitis are *idiopathic* (abacterial prostatitis). Depending on the status of the expressed prostatic secretions (EPS), these patients with chronic abacterial prostatitis are classified further as a) nonbacterial prostatitis if the EPS is purulent (leukocyte count elevated) or b) prostatodynia if the EPS is not purulent. To date there is no standardized method of diagnosis and treatment of this condition. As noted recently by Nickel and Sorensen (4), the problems and frustrations found in clinical trials investigating therapies for nonbacterial prostatitis are that

"our definition of the syndromes is unclear, the etiology is obscure, the relevance of the only objective finding we have (leukocytosis) is unknown, symptoms are highly variable, the natural history of the disease has not been adequately studied and the numbers in most clinical trials, including ours, are small".

They concluded that "since the symptoms are paramount in these patients, evaluation of response can only be achieved by using reproducible and validated symptom evaluation instruments."

Recognizing the importance of addressing problems in the diagnosis and treatment of prostatitis, a National Institute of Diabetes, Digestive and Kidney (NIDDK) Diseases Workshop on Chronic Prostatitis (5) was held in Bethesda, MD on December 7-8, 1995, from which the new consensus working definition and classification of prostatitis syndromes (NIDDK reference standard) for research studies on these diseases and disorders was summarized as follows:

1. *Acute bacterial prostatitis* is an acute infection of the prostate.
2. *Chronic bacterial prostatitis* is a recurrent infection of the prostate.
3. *Chronic nonbacterial prostatitis/chronic pelvic pain syndrome* (CPPS), where there is no demonstrable infection. Subgroups of this class are:
  - 3.1 *Inflammatory chronic pelvic pain syndrome*, where white cells are found in the semen, expressed prostatic secretions (EPS), or voided bladder urine-3 (VB-3).
  - 3.2 *Non-inflammatory chronic pelvic pain syndrome*, where white cells are NOT found in the semen, EPS, and VB-3.
4. *Asymptomatic inflammatory prostatitis* (AIP), where there are no subjective symptoms but white blood cells are found in prostate secretions or in prostate tissue during an evaluation for other disorders.

Patients in Categories 1-3 are characterized by chronic pain; however, unlike patients in Category 1 & 2, patients with Category 3 prostatitis do not have any detectable infection of the prostate as determined by conventional microbiological techniques. Abnormalities in the EPS are the primary

1 objective features of Category 3 prostatitis and chronic pain is the primary subjective symptom. The  
2 majority of patients with chronic prostatitis are Type 3. (3)

3  
4 The occurrence and persistence of pain as a primary presenting symptom is an important aspect of  
5 both diagnosis and outcome evaluation. In the recent review article in *Pain* by Egan and Krieger (6),  
6 they note that “chronic abacterial prostatitis is remarkably similar to chronic pain syndromes”, and  
7 accordingly they make the case for therapy based on multidisciplinary approaches to pain  
8 management, rather than the traditional ‘organ system’ approach. Many therapies have been tried for  
9 chronic prostatitis, with a primary focus on improving bladder outlet resistance. However, the  
10 general consensus among clinical urology research investigators conducting therapy trials involving  
11 chronic prostatitis patients is well reflected in the recent summary of Nickel and Sorensen (4) that

12 "more research and larger clinical studies in the nonbacterial chronic prostatitis syndromes  
13 are urgently required."  
14

15 In response to these growing concerns about the diagnosis and treatment of Chronic Prostatitis, the  
16 NIDDK funded the Chronic Prostatitis Clinical Research Network (CPCRN), comprised of six (6)  
17 Clinical Research Centers (CRCs) and a Data Coordinating Center (DCC), effective October 1, 1997.  
18 The primary research questions to be addressed by the CPCRN will encompass the diagnosis,  
19 etiology, natural history and prognosis, and the development of treatment strategies focused on  
20 Chronic Abacterial Prostatitis - Chronic Pelvic Pain Syndrome (CPPS). In support of these broad  
21 research goals, the CPCRN formed Working Groups to coordinate the development of a longitudinal  
22 Chronic Prostatitis Cohort (CPC) Study, the development and validation of a symptom severity index  
23 for CPPS, as well as other laboratory and clinical outcome measures. Ultimately, the goals of the  
24 CPCRN are to conduct well-controlled, multicenter epidemiological studies and therapeutic trials  
25 aimed at providing definitive answers to the unresolved questions of diagnosis and treatment of  
26 CPPS.  
27

## **2.1 SPECIFIC AIMS**

The goal of the Chronic Prostatitis Cohort (CPC) Study is to assemble and follow a cohort of patients with Chronic Pelvic Pain Syndrome (CPPS). The specific aims are to

- i) better define the condition Chronic Prostatitis (CP) or Chronic Pelvic Pain Syndrome (CPPS);
- ii) develop techniques to aid in the diagnosis of CP;
- iii) characterize the patient with CP;
- iv) study the natural history and prognosis of patients with CP;
- v) set the stage to conduct epidemiological studies to address etiologic hypotheses;
- vi) set the stage to begin clinical trials and offer effective therapy for CP.

To implement this CPC Study, a centralized, standardized registry containing data on patients at baseline screening and longitudinal follow-up will include demographic and diagnostic information, dietary habits, patient and family medical history, symptoms, and treatments and their outcomes. In addition, serum and prostatic fluid specimens will be stored in specimen banks for future use by qualified investigators.

## **2.2 STUDY TIME FRAME**

A pilot study to test patient recruitment and screening procedures at the Clinical Research Centers (CRCs), data collection and data entry procedures, and internet communications between the CRCs and the DCC will begin on October 12, 1998. (Two patients in each of the 6 Clinical Centers will be recruited for the pilot study). The full-scale CP Cohort study will begin on November 9, 1998, and recruitment of approximately 630 patients will continue for 3 years until 2001.

## **2.3 STUDY POPULATION**

The study population of particular interest is the group of male patients with symptomatology consistent with Chronic Prostatitis (CP) or Chronic Pelvic Pain Syndrome (CPPS). Any potential study participant must meet a set of basic criteria before being considered a candidate for the complete screening process. Patients' clinical signs and symptoms will be assessed, documented and treated in a manner that is consistent with the standards of good urological practice. As such, each patient will be evaluated as deemed appropriate prior to consideration for CPC Study enrollment.

### ***2.3.1 Inclusion Criteria***

Any patient satisfying all of the following criteria will pass the screening for inclusion:

1. Male.
2. Having symptoms of discomfort or pain in the pelvic region for at least three months duration within the last six months.

### 2.3.2 *Deferral Criteria*

There are several physical conditions for which a patient will be deferred from entry into the CPC Study. Once it is formally ascertained that the condition is not present or has subsided, the patient will be reconsidered for entry into the CPC Study. The following list identifies the conditions for deferment and the criteria that a patient must meet in order to be evaluated further for entry into the study:

1. If a patient has been treated with antimicrobial agents within the last three months, he will be deferred until he has been treatment free for three months. This period of time will include the three months prior to screening.
2. If a patient has had a positive urine culture in the past 3 months (as reported by the patient), or has had a positive urine culture laboratory value of >100,000 CFU/ml, the patient will be deferred until he is without the condition for 3 months;
3. If a patient has any of the following sexually transmitted diseases; Gonorrhea, Chlamydia, Mycoplasma, Trichomonas, he will be deferred until he has been off treatment and symptom free for three months.
4. If a patient has had a prostate biopsy within the last three months, he will be deferred until three months from the date of the procedure.
5. If a patient has been told by a health care professional that he had epididymitis within the last three months, he will be deferred until he has been off treatment and symptom free for three months.
6. If a patient has been diagnosed with or treated for symptomatic Genital Herpes in the past twelve months, he will be deferred until he has been symptom free for a twelve-month period.

### 2.3.3 *Exclusion Criteria*

Any patient satisfying any one of the following criteria will not be eligible to participate in the CPC Study. Exclusion criteria will not be ongoing throughout the study. Patients experiencing any of the exclusion criteria during the follow-up phase of the study will continue to be tracked and included in the cohort study. However, it will be noted in follow-up data if a patient has developed any of the exclusion criteria.

1. Patients with a history of prostate, bladder or urethral cancer.
2. Patients with the following Inflammatory Bowel Diseases: Crohn's Disease and Ulcerative Colitis, will be excluded from the CPC Study. Patients with Irritable Bowel Syndrome will not be excluded from the study.
3. Patients who have been treated with BCG.
4. Patients with unilateral orchalgia, without pelvic symptoms.
5. Patients with an active urethral stricture.

- 1 6. Patients with a neurological disease or disorder affecting the bladder.
- 2
- 3 7. Patients with a history of TURP, TUIP, TUIBN, TUMT, TUNA, balloon dilation, or any other
- 4 prostate surgery or treatment such as cryotherapy or thermal therapy.
- 5
- 6 8. Patients with a history of pelvic radiation, systemic or intravesical chemotherapy.
- 7
- 8 9. Patients with a neurological impairment or psychiatric disorder preventing their understanding of
- 9 consent and their ability to comply with the protocol.
- 10

## 11 **2.4 SAMPLE SIZE/POWER CONSIDERATIONS FOR THE CPC STUDY**

12 Each Clinical Research Center (CRC) will enroll approximately 35 patients with CP/CPPS into the  
13 CPC Study each year, beginning on November 9, 1998 (grant year 02), and continuing enrollment  
14 until August 31, 2001 (end of grant year 04). Assuming that each of the six (6) CRCs attain this  
15 accrual goal, the CPC Study will net 630 (35/yr. x 3 yrs. x 6 CRCs) patients with CP/CPPS.

16 Although sample size justifications for such a multi-purpose cohort study require specifications of  
17 study design parameters for a wide variety of hypotheses, we considered investigating baseline  
18 associations in the CPC Study under a range of plausible study design characteristics (see Appendix  
19 A).

20  
21 In addition to the measures for baseline comparisons described below, symptoms and other  
22 potentially time-dependent outcomes (*e.g.*, white blood cell counts) will be measured repeatedly over  
23 time (*e.g.*, at the baseline visit, 1, 2, 3, 6, 9 and 12 months during the first year). It is expected that  
24 there may be trends towards improvement in symptoms due to an “intervention effect” of study  
25 participation, which will level off by three to six months after study initiation for each patient. Thus,  
26 once symptoms have stabilized within each patient, these repeated measurements may serve as  
27 replicates such that this cohort study design will have increased power to detect associations both  
28 among the individual components of the symptom index and between symptoms and these other  
29 measures. Appropriate clustered (“mixed effects”) data models will be used to account for the  
30 within-patient replications in these analyses

### 31 32 **2.4.1 Baseline Associations: Binary Risk Factor**

33 Suppose the CPC Study patients are classified according to the presence or absence of a symptom  
34 (*e.g.*, pain exceeding a selected threshold) and a potential risk factor such as presence of a laboratory-  
35 based marker, such as elevated white count in EPS. Then, as displayed in Table 2 (Appendix A),  
36 assuming two-sided hypothesis testing at the 5% level, power of 80% for detecting odds ratios of 2.0  
37 and 2.5, and proportions of patients with the symptom present ranging from 10% to 50%, the  
38 required sample size (after adjustment for clustering among clinical centers) ranges from 1,028 to  
39 252. For example, these sample size projections in Table 2 indicate that baseline associations with  
40 odds ratios of 2.0 or greater can be detected with 80% power with a total sample size of 602  
41 evaluable patients, provided that the selected symptom has a prevalence rate of at least 20%. For our  
42 proposed cohort size of 630 patients, if the prevalence of the selected symptom is less than 20%,  
43 these results in Table 2 indicate that the power may still approach 80% to detect associations with  
44 odds ratios somewhat larger than 2.5, even if the prevalence rate is only 10%.

### 2.4.2 *Baseline Associations: Continuous Risk Factor*

Suppose the CPC Study patients are classified according to the presence or absence of a symptom (e.g., pain exceeding a selected threshold) and a potential risk factor measured on a continuous scale, such as the level of a laboratory-based marker, such as the white blood cell count in EPS. Then, as displayed in Table 3 (Appendix A), assuming two-sided hypothesis testing at the 5% level, power of 80% for detecting standardized effect sizes of 0.2, 0.3, 0.4 and 0.5, and proportions of patients with the symptom present ranging from 10% to 50%, the required sample size (after adjustment for clustering among clinical centers) ranges from 3,273 to 190. For example, these sample size projections in Table 3 indicate that for investigating standardized baseline mean differences of 0.4, a total sample size of 462 evaluable patients is required for symptoms with a prevalence of at least 20%, whereas a total sample size of 819 evaluable patients is required for symptoms with a prevalence of at least 10%. These results in Table 3 indicate that our proposed cohort size of 630 patients will be more than adequate to detect effect sizes of 0.3 s.d. units, provided the prevalence of the selected symptom is at least 30%, and effect sizes of 0.5 s.d. units, even if the prevalence of the selected symptom is only 10%. Conversely, these same calculations apply to analyses in which continuous symptom measures will be compared between two groups defined by a dichotomous baseline grouping measure.

### 2.4.3 *Longitudinal Effects: Comparing Change Over Time*

The primary rationale for collecting the longitudinal data within this CPC cohort study is to characterize the variability over time in the key symptoms and laboratory measures, in preparation for designing and conducting randomized clinical trials in patients with CP/CPPS. Since this CPC study design does not include a standard intervention, the resulting data will provide estimates for within-patient and between-patient variability in the natural treated (*viz.*, usual care) history of CP/CPPS. Effects of limited institution-specific treatment trials will be accounted for in the statistical analyses by adjustments for clinical center effects and identification of treatment assignments. In addition, as mentioned above, evaluation of changes (if any) over time will allow assessment of the magnitude of an intervention effect, providing minimum estimates of placebo effects for future randomized trials.

Although specific longitudinal hypotheses have not been identified in advance, hypothesis-generating analyses focusing on differential patterns of change over time in symptoms or laboratory measures for subgroups identified by baseline factors will benefit from the increased statistical power due to the repeated measures and the within-patient correlations.

## **2.5 INFORMED CONSENT**

At the start of Screening Visit #1, after the Research Coordinator (RC) determines that a patient meets the inclusion criteria, but prior to the thorough screening process, an informed consent will be obtained from each patient. The parent or guardian of patients under 18 years of age will be asked to sign the informed consent form. Only one informed consent will be required for each patient. That is, at Screening Visit #1, the patient will provide informed consent for the baseline screening procedures, as well as for all follow-up procedures. Prior to obtaining a patient's informed consent, participants will be informed of all aspects of the study, including baseline screening procedures, follow-up procedures, assurance of patient confidentiality, and potential risks and benefits to the patient (see Appendix B).

### **3. STUDY PLAN**

The CPC Study comprises two distinct phases for each participating patient: i) the *screening phase* and ii) the *longitudinal follow-up phase* (see Appendix C). The screening phase, which assesses a patient's eligibility to participate in the CPC Study, comprised of two to three clinic visits scheduled as closely together as possible. Ideally, all screening clinic visits will be completed in a 2-3 week period.

Screening criteria must be completed within 30 days of the initial visit in order for a patient to remain eligible for study participation. Any patient failing any of the inclusion or exclusion criteria will be treated according to usual clinical care, but will not be eligible to participate in the follow-up phase.

Any patient passing all of the inclusion, deferral and exclusion criteria will receive all baseline screening tests/procedures and will be eligible to participate in the longitudinal follow-up phase.

Patients participating in this phase will be followed until the close of the CPC Study, with six contacts during year 01, four by telephone (at 1, 2, 3, and 9 months post-screening) and two times by a physician's office visit (at 6 and 12 months post-screening). Duration of follow-up will vary depending upon the patient's study enrollment date. In subsequent years, patients will be followed by two physician visits and two telephone contacts. The phone calls will take place during months 3 and 9 of every patient-year, and the clinic visits on months 6 and 12 of every patient-year (see Appendix D).

#### **3.1 PATIENT RECRUITMENT**

Patient recruitment will be conducted through the urology clinic at each of the participating Clinical Research Centers (CRCs). Patients referred to the CRCs with symptoms suggestive of CP/CPSP will be introduced to the CPC Study by the Research Coordinator and by a one-page flyer describing the study (see Appendix E). In an effort to recruit minority patients, participating CPC Study centers will seek the participation of primary care physicians, clinic sites and other referral sources not previously included in the CPC Study network. Potentially eligible patients will then be asked whether they are interested in participating in the study. The CPC Study will identify patients by referral source and zip code in order to more fully describe the study population.

[figure not shown]
#### **3.2 PATIENT SELECTION**

Initially every potential study participant will undergo a series of screening procedures that take approximately 2 - 3 weeks to complete. The screening phase entails at least two clinic visits. The screening process may take three visits, depending on procedure completion. The data collected and diagnostic procedures completed during this phase are identified below (see Sections 3.2.1 and 3.2.2), in the order in which they will be obtained or undergone. The order of the procedures identified below has been selected to ensure that eligibility criteria checked by non-invasive methods precede those checked by more invasive methods, and to provide a balance of patient comfort and timeliness.

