32 Each patient will undergo a focused physical examination. This examination will include an  
33 abdominal exam, external genital exam, rectal exam, prostate exam, and perineal exam.  
34
- 35 8. *Urinalysis, urine and EPS specimens for microscopy and culture.*  
36 Each patient will provide the research staff with 3 urine specimens and an EPS (expressed  
37 prostatic secretion) specimen for analysis and culture. The urine specimen will be collected via  
38 the classic “four-glass test” described in Meares and Stamey (7). The FGT will be attempted  
39 one time only at Screening Visit #1 and at each subsequent clinic visit. Patients must be able to  
40 provide at least one of the following samples: EPS, VB3 or a semen sample, at SV1 or SV2, to  
41 be included in the study.

1 The results from the EPS culture and the post-EPS urine (VB3), if available, will be compared with the findings from the 1st voided urine (VB1) and the midstream urine (bladder specimen or (VB2). A macroscopic urinalysis will be completed to quantify hemoglobin, protein, and glucose levels, and a microscopic urinalysis will be completed to quantify white blood cells, red blood cells and yeast. All specimens will be cultured for 5 days, with results recorded at 48 hours and 5 days.

14 Although the urinalysis will be performed at the respective CRC, all centers will be required to use the same brand of dipstick (see Appendix F). An alternative (to the Uricult paddle) laboratory plating procedure, will also be utilized at the clinical centers.

15  
16  
17  
18  
19 9. *Serum Sample collection.*

20 Up to 10 mls of venous blood (which amounts to approximately 1 tube of blood), will be  
21 collected from each patient. The specimen will be stored at the CRC Laboratory in the frozen  
22 serum bank for future research use (see Appendix G).

23  
24 10. *Visit close-out.*

25 i. Appointment scheduling. An appointment will be made for Screening Visit #2.

26  
27 ii. Concomitant medications. Each patient will receive instructions from the RC to bring  
28 to Screening Visit #2 all of the over-the-counter and prescribed medications that he is  
29 currently taking.

30  
31 **3.2.2 Screening Visit #2**

32 During this screening visit, each patient will complete the questionnaires and/or undergo the  
33 examinations described below.

34  
35 1. *1-Day Voiding Log.*

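### Section 3.2 fixes an order at Screening Visit #1 that puts the rectal and prostate examination before the four-glass test, so the reference urines VB1 and VB2 are collected after palpation

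*Protocol*

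**What the plan says.** Section 3.2 tells sites how to read the lists that follow: the data and procedures of 3.2.1 and 3.2.2 appear "in the order in which they will be obtained or undergone". It gives reasons for the order, namely that "eligibility criteria checked by non-invasive methods precede those checked by more invasive methods", together with patient comfort and timeliness. Specimen integrity is not among them.

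In section 3.2.1, item 7 is a focused physical examination covering "abdominal exam, external genital exam, rectal exam, prostate exam, and perineal exam". Item 8 is headed "Urinalysis, urine and EPS specimens for microscopy and culture" and collects three urines and EPS by the classic four-glass test, cited to its source publication. Under the same item, the EPS culture and the post-EPS urine (VB3), "if available, will be compared with the findings from the 1st voided urine" (VB1) and the midstream urine (VB2). The test is to be attempted "one time only at Screening Visit #1 and at each subsequent clinic visit".

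The follow-up lists differ from each other. Section 3.3.2 (months 6, 18 and 30) puts the specimens at item 3 and the physical examination at item 4. Section 3.3.3 (months 12, 24 and 36) puts the examination at item 4 and the specimens at item 5. In both, the extent of the examination is left to the physician.

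**The concern.** The comparison in item 8 sets specimens obtained by or after expression of prostatic secretion (EPS, VB3) against urine meant to represent the urethra and bladder before expression (VB1, VB2). It is informative only if the reference urines are free of prostatic material. If the gland has already been palpated, some secretion may have reached the urethra. VB1 would be the specimen mainly affected, since it is voided first and VB2 follows it in midstream. The difference between the two sets of specimens could then shrink for a procedural reason.

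At stake is the interpretability of the before-and-after-expression comparison at baseline. It cannot be repaired in analysis, because the order of examination and voiding is a condition of collection, and only one attempt is allowed at that visit.

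**Working it through.** No arithmetic applies: the protocol gives no figure for this point and no estimate of carry-over. The check is a reading of the sections side by side.

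| Visit | Physical examination | Specimens | Order listed | Is list order declared to be order of performance? |
|---|---|---|---|---|
| Screening Visit #1 (3.2.1) | item 7, rectal and prostate exam named | item 8 | exam first | Yes, by 3.2 |
| Brief visit, months 6, 18, 30 (3.3.2) | item 4, at the physician's discretion | item 3 | specimens first | No |
| Yearly visit, months 12, 24, 36 (3.3.3) | item 4, at the physician's discretion | item 5 | exam first | No |

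1. *Is the order a rule or just a list?* At screening it is a rule. Section 3.2 says the list is sequential and that the sequence was chosen. The opening paragraph of 3.2.1 also names the physical examination ahead of urinalysis and urine culture.

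2. *Does anything in the text at hand override it for VB1 and VB2?* No. Item 8 identifies the test by citation and describes which specimens are compared. It does not say that the first two urines precede the item 7 examination.

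3. *Which specimens does the order touch?* EPS and VB3 follow expression whichever order is used. VB1 and VB2 are the ones whose status changes, from before palpation to after it.

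4. *Does the protocol's own rationale require the exam first?* No. Voiding urine is less invasive than a rectal examination, and a positive urine culture is itself a deferral criterion (section 2.3.2, criterion 2). Collecting VB1 and VB2 first therefore fits the non-invasive-before-invasive principle at least as well as the listed order.

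5. *Which results depend on VB1 and VB2?* The comparison in item 8 does. The split of category 3 in section 1 does not: it uses white cells in semen, EPS or VB3 and makes no reference to VB1 or VB2. The specimen requirement for enrolment (at least one of EPS, VB3 or semen) does not use them either.

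6. *How many men are covered?* The order rule applies to every man screened. Planned enrolment is 35 × 3 × 6 = 630 (section 2.4). That is the number collected under the rule, not the number whose comparison would be distorted.

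**The case against.** The strongest reply is that the detailed procedure lies elsewhere. Item 8 adopts a published method by citation, and the contents page lists an Appendix F for the four-glass test and an Appendix G for patient procedures, neither of which is in the text at hand. Either may say how palpation, voiding and massage relate, and section 3.2 may have been ordering whole items rather than the steps of specimen collection. This stands as a caution: no one can assert from these pages that sites actually collected specimens in the wrong order, or that the protocol contradicts Appendix F. It does not remove the point. Section 3.2 makes a positive statement about sequence, and if an appendix gives another sequence the two need to be reconciled.

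A second reply is that no passage says an examination short of massage expresses secretion or contaminates the voided urine. That is correct. The mechanism is an inference, and the supportable wording is that the comparison may be blurred.

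Several stronger readings are tempting and should be resisted:

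- *A numerical ceiling on the contrast.* A reader might reason that if the examination releases some fraction of the later yield, the after/before ratio is capped at the reciprocal of that fraction. The fraction is not given. The cap also assumes equal dilution, whereas EPS is expressed secretion and VB1 and VB2 are urine, and one fraction could not serve both a first-voided and a midstream specimen.
- *Misclassification of inflammatory against non-inflammatory disease, or loss of the objective basis for the first two aims.* The classification does not use VB1 or VB2, and section 1 names EPS abnormalities, not this comparison, as the primary objective features.
- *An artificial alternation in the follow-up series.* The order statement covers only 3.2.1 and 3.2.2. The follow-up specimen entries refer back to a form described under Screening Visit #1, so those lists can be read as lists of forms, and a prostate examination is not assured at those visits. The follow-up order is unspecified rather than fixed wrongly.

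**Conclusion.** The point holds in a limited form. At Screening Visit #1 the protocol prescribes, by an explicit statement of order, that the rectal and prostate examination precede collection of the urines that serve as reference for EPS and VB3. This may carry prostatic secretion into the reference urine and may weaken the comparison at baseline. The size of any effect is unknown from the documents.

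The conclusion rests on two assumptions: that sites follow list order as section 3.2 tells them to, and that palpation can release some secretion. If Appendix F already places VB1 and VB2 first, what remains is a conflict of wording to be reconciled. The change is worth making because it costs little and the collection conditions cannot be restored afterwards.

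**What to change.** - In section 3.2.1, state that VB1 and VB2 are collected before any rectal or prostate examination, with EPS and VB3 obtained after. The remaining parts of item 7 can stay where they are.
- Check this against Appendix F and reconcile the two so that one sequence appears in both places.
- In sections 3.3.2 and 3.3.3, state the same specimen sequence for any visit at which a rectal or prostate examination is done, so that baseline, brief-visit and yearly specimens are collected under like conditions.

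The cost is an edit to three sections and a note to sites. Procedures, visits and staff are unchanged.
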